## 9. STATISTICAL CONSIDERATIONS AND DATA ANALYSES

### 9.1 Sample Size Determination

Approximately 130 **178** healthy females within the ages of 30 and 60 years with Fitzpatrick Skin Classification II-IV and moderate to advanced photo-damaged skin will be screened to randomize 80 **100** subjects to ensure approximately 60 **80** subjects (**30 40** subjects per group) successfully complete the study. The sample size is based on clinical considerations and literature precedent [Narurkar, Schalka, Sulimovic, Kim].

~~With 30 subjects per treatment group, a change from baseline in TEWL at least half the magnitude of the standard deviation (e.g. assume std=4 (ref. **CCI** [REDACTED]), and 2.1 point mean change from baseline) can be detected at two-sided alpha=0.05 with 80% power.~~

**THE FIRST 10 SUBJECTS WERE MIS-ALLOCATED TREATMENT. TO PROTECT THE STATISTICAL POWER OF THE STUDY FOR THE SECONDARY TEWL ENDPOINT, 20 ADDITIONAL SUBJECTS WILL BE RECRUITED INTO THE STUDY. WITH 100 SUBJECTS RANDOMISED, 80 SUBJECTS (40 SUBJECTS PER GROUP) ARE EXPECTED TO COMPLETE THE STUDY.**

**WITH 40 SUBJECTS PER TREATMENT GROUP WITH 5 SUBJECTS PER GROUP RECEIVING THE INCORRECT TREATMENT DUE TO MIS-ALLOCATION, A WITHIN CHANGE FROM BASELINE IN TEWL OF 1.83 CAN BE DETECTED AT TWO-SIDED ALPHA=0.05 WITH AN SD=4.053 AND 80% POWER.**

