## 2. OBJECTIVE(S) AND ENDPOINT(S)

Objective(s)	Endpoint(s)
Primary	
Assessment of the local tolerance of the test product in subjects who have undergone a 70% Glycolic Acid facial peel	Evaluator (Dermatologist) global assessment of tolerance
Secondary	
Assessment of skin recovery (change from baseline) over a period of 14 days in subjects who have undergone a 70% Glycolic Acid facial peel	Combined (sum of) Evaluator (Dermatologist) scores for signs/symptoms of erythema, edema, desquamation and dryness  Individual Evaluator (Dermatologist) scores for erythema, edema, desquamation and dryness  Combined (sum of) subject self-assessment scores for redness, pain, stinging/burning, itching, tightness and dryness  Individual subject self-assessment scores for redness, pain, stinging/burning, itching, tightness and dryness  Instrumental measurement of barrier function (Tewameter) and moisturisation (Corneometer)  Subject global self-assessment
Assessment of skin recovery (change from baseline) between treatment groups.	All assessments and measurements listed above

Document Name	Protocol 206827 CCI doc	Document Identifier	Effective Date
Type	Version		
eldo controlled	4.0; Most-Recent; Effective; CURRENT	090032d580d98eb9	15-Sep-2017 09:27:15

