#### **9.2.2. Exclusion of Data from Analysis**

No data will be excluded from any analyses.

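### The power claim for TEWL after the mis-allocation covers only the within-group change; for the between-group comparison, 40 per group analysed as assigned detects less than 30 per group correctly treated

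*Protocol*

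**What the plan says.** Protocol section 9.1 reports that the first ten subjects were allocated the wrong treatment and gives the reason for the increase: "TO PROTECT THE STATISTICAL POWER OF THE STUDY FOR THE SECONDARY TEWL ENDPOINT, 20 ADDITIONAL SUBJECTS WILL BE RECRUITED INTO THE STUDY". The calculation that follows starts from "WITH 40 SUBJECTS PER TREATMENT GROUP WITH 5 SUBJECTS PER GROUP RECEIVING THE INCORRECT TREATMENT DUE TO MIS-ALLOCATION" and concludes that "A WITHIN CHANGE FROM BASELINE IN TEWL OF 1.83 CAN BE DETECTED AT TWO-SIDED ALPHA=0.05 WITH AN SD=4.053 AND 80% POWER". It is a within-group statement. The superseded calculation, for 30 per group, was also within-group: a mean change from baseline of 2.1 with SD 4 and 80% power.

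Section 2 lists two secondary objectives. One is recovery from baseline over 14 days. The other is "Assessment of skin recovery (change from baseline) between treatment groups", covering all the listed measurements, Tewameter included. Section 9.3.3 gives the second its own test (t-test or Wilcoxon rank sum) and describes it as explored.

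On handling, section 9.2.1 puts every randomised subject in the ITT population, and section 9.2.2 says "No data will be excluded from any analyses". The model in 9.1 itself counts the mis-allocated women among the 40 per group.

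**The concern.** Section 9.1 speaks of power for the TEWL endpoint without qualification, but its arithmetic addresses one of the two TEWL questions the protocol asks. The within-group change mixes any product effect with natural healing. Section 3.4 expects barrier function to return to normal 24 to 48 hours after the peel, and gives no reason to think this is confined to one arm. Only the comparison with the no-treatment arm can point to the product.

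That comparison is also the one the mis-allocation hurts most. Five women per arm received the other arm's regimen, so each arm's mean is pulled towards the other. A reader of 9.1 would take it that the enlargement repaired the damage to TEWL. If it did not, a null between-group result could be read as evidence of no product effect when part of the cause is dilution.

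**Working it through.** **Inputs.** From 9.1: two-sided alpha 0.05, 80% power, 40 per group, five per group wrongly treated, change 1.83, SD 4.053. From the superseded calculation: 30 per group, SD 4, change 2.1. Power is from the noncentral t distribution.

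**1. The plan's own figures (one-sample t, noncentrality = change / SD × √n).**
- n = 40, change 1.83, SD 4.053: power 79.5%. The exact detectable change is 1.84.
- n = 30, change 2.1, SD 4: power 79.4%.

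Both reproduce, and within-group power as 9.1 defines it is unchanged. Read as two-sample tests, the same figures would have only 51% (1.83, 40 per group) and 52% (2.1, 30 per group), so neither was a between-group calculation.

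**2. Between-group benchmark.** Two-sample t, noncentrality = D / SD × √(n/2). With 30 per group correctly treated and SD 4, 80% power is reached at D = 2.94. The protocol does not state this figure; it is what the superseded design would have delivered.

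**3. Effect of the crossover.** Let D be the true difference between product and no treatment. With 5 of 40 on the other regimen in each arm, the expected difference as assigned is D × (35/40 − 5/40) = D × 30/40 = 0.75 D. Mixing two means within an arm also widens its SD, to √(16 + 0.125 × 0.875 × D²). At D = 2.94 this is √(16 + 0.109 × 8.66) = 4.12. The lower power in each range below uses the widened SD; the higher holds SD at 4.

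| Handling | Power at D = 2.94 | D detectable at 80% |
|---|---|---|
| 30 per group, all correctly treated | 80% | 2.94 |
| 40 per group, 5 crossed over per arm, as assigned | 66–68% | 3.4–3.5 (3.38 to 3.52) |
| 40 per group, 4 crossed over per arm, as assigned | 72–74% | 3.2–3.3 (3.17 to 3.27) |
| 35 per group, the ten left out | 86% | 2.72 |
| 40 per group, by product received | 90% | 2.54 |
| 30 per group, 5 crossed over per arm, none added | 44–46% | – |

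The third row covers the case where the mis-allocated women drop out at the overall rate in 9.1 (100 randomised, 80 completing), leaving four of five per arm. There the difference shrinks to 0.8 D.

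As a rough check with SD held at 4, the effective size as assigned is 40 × 0.75² = 22.5 per group, below 30.

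**4. What 1.83 refers to.** It is a mean change over all 40 analysed. If the mis-allocated women in a group changed less than the others, the others must have changed by more than 1.83 to give that mean. In the extreme case of no change at all in the five, the correctly treated 35 would need 1.83 × 40/35 = 2.09. If the five changed as much as the rest, there is no such gap. The protocol does not say which it assumed.

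**The case against.** The strongest reply is that 9.1 keeps the promise it makes. Both power statements are within-group, the amended one is correct, and within-group power is held (79.5% against 79.4%). The between-group comparison is only explored, was never powered, and had just 52% power at a difference of 2.1 under the superseded design. The benchmark of 2.94 is solved backwards. The primary endpoint and the success rule in 9.2.3 do not involve TEWL, and the 20 added subjects clearly improve on adding none. Analysis sets for mis-allocated subjects are often left to the SAP, which is not to hand.

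Most of this stands, and it limits the weight of the point. It does not rescue the unqualified wording of the claim in 9.1, because the between-group TEWL comparison is a listed objective and 9.2.2 fixes in the protocol that nothing is excluded.

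The per-protocol set does not supply the remedy either. Section 9.2.1 requires at least one application of test product for entry, which correctly treated Group II women never receive.

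Three stronger readings are tempting and are not supported:
- **That 1.83 is miscalculated.** It reproduces.
- **That 1.83 is the old 2.1 diluted, so 9.1 should say 2.1.** The numbers are close (2.1 × 35/40 = 1.8375; mixture SD 4.06 against the stated 4.053). But the protocol gives no derivation, a plain one-sample calculation at n = 40 returns 1.84 with no dilution, and the restatement would need zero change in mis-allocated women, which fits badly with the recovery expected in section 3.4.
- **That product received should be the main analysis.** This departs from ITT after the error is known, and whether the groups would still be randomised depends on how the error arose, which the protocol does not say.

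**Conclusion.** The point holds in a limited form. Section 9.1 supports its power claim for the within-group TEWL change only. For the between-group comparison, keeping the ten women as assigned leaves 40 per group able to detect a difference of 3.4 to 3.5 at 80% power, worse than the 2.94 available with 30 per group correctly treated. Power at 2.94 is 66 to 68%, or 72 to 74% if four of five per arm complete.

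This assumes SD 4 for the change in both arms, a t-test, 40 completers per group, a full exchange of regimens in the mis-allocated women, and analysis by assigned group. The last is what 9.1, 9.2.1 and 9.2.2 together imply, although 9.3.3 names no population. The consequence falls on a secondary, exploratory comparison. It does not touch the primary tolerance endpoint.

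**What to change.** **Section 9.1.** State that the power claim applies to the mean within-group TEWL change over all 40 analysed per group, and that 1.83 is not the change detectable in correctly treated women alone if mis-allocated women change less. Add that the between-group difference detectable at 80% power, as assigned, is about 3.4 to 3.5 (SD 4, all ten completing).

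**Sections 9.2.2 and 9.3.3.** Keep the as-assigned ITT analysis. Add a pre-specified supportive analysis of TEWL and the other efficacy comparisons that leaves out the first ten subjects (detectable TEWL difference 2.72, 35 per group), or groups them by product received (2.54, 40 per group), or both. Document the cause of the mis-allocation: the product-received version is a valid randomised comparison only if the error is shown to be one of list handling and not a choice made subject by subject. Section 9.2.2 needs matching wording so that the supportive analysis does not contradict it.

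**Section 9.2.1.** Reword the per-protocol definition so that Group II is not required to have applied test product.

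**Cost.** Wording and one small extra analysis, with no further subjects. The stated sensitivity for TEWL becomes less favourable than 9.1 now suggests.

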### 9.2. General Considerations

#### 9.2.1. Definition of Analysis Populations

All randomized subjects will be included in the intent-to-treat (ITT) population. All subjects with at least one application of product in the test phase (i.e. test product for subjects in Group I or sunscreen for subjects in Group II) will be included in the Safety population.

Document Name	Protocol 206827 CCI doc		
Type	Version	Document Identifier	Effective Date
elido controlled	4.0; Most-Recent; Effective; CURRENT	090032d580d98eb9	15-Sep-2017 09:27:15
Reason For Issue	Auto Issue		

Subjects will be considered eligible for a Per Protocol (PP) population if they were randomized, received at least one application of test product, had at least one post-procedure, post-treatment assessment available and were compliant with both test and washout products post-procedure. Other considerations for eligibility for the PP population including but not limited to use of concomitant medications will be detailed in the Statistical Analysis Plan prior to database unblinding.

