## PROTOCOL AMENDMENT PAGE

Details of all amendments should be recorded in the table below. Affected sections should be listed in the table; the actual amendment/ change should be made in the relevant section of the main protocol.

To highlight the change, the following features will be used:

To **add** text: Use of **CAPITAL LETTERS, BOLD AND UNDERLINE**

To **delete** text: Use of Strikethrough e.g. ~~strikethrough~~

Amendment No. & New Protocol Version No.	Type of Amendment	Reason for Amendment	Other Documents Requiring Amendment	Section(s) Amended	PI Amendment Agreement Signature & Date
Amendment No.: 1	Non-Substantial/Minor 	To increase the target number of randomised subjects from 80 to 100 in response to the first 10 subjects being incorrectly randomised into the study.	Informed Consent  Yes  No Safety Statement  Yes  No CRF  Yes  No	Protocol synopsis (page 23)  Section 3.3 (page 33)  Section 9.1 (page 82)	Signature: PPD
Protocol Version No.: 4	Substantial/ Major 				Date: PPD
Amendment No.: 2	Non-Substantial/Minor 	To update the Data Manager details for the study.	Informed Consent  Yes  No Safety Statement  Yes  No CRF  Yes  No	Summary information (page 3)	Signature: PPD
Protocol Version No.: 4	Substantial/ Major 				Date: PPD

 GlaxoSmithKline	Document NCCI	Protocol 206827 doc		
	Type	Version	Document Identifier	Effective Date
	eldo_controlled	4.0; Most-Recent; Effective; CURRFNT	090032d580d98eb9	15-Sep-2017 09:27:15
	Reason For Issue	Auto Issue		

 GlaxoSmithKline	Document No	CCI	Protocol 206827 doc		
	Type	Version	Document Identifier	Effective Date	
	elido_controlled	4.0: Most-Recent; Effective; CURRENt	090032d580d98eb9	15-Sep-2017 09:27:15	
	Reason For Issue	Auto Issue			

Amendment No. & New Protocol Version No.	Type of Amendment	Reason for Amendment	Other Documents Requiring Amendment	Section(s) Amended	PI Amendment Agreement Signature & Date

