#### **6.4.10. Supervised Sunscreen Application**

All subjects will undergo supervised sunscreen application. The Investigator or designee will oversee application of the SPF 50 sunscreen. Product application will be recorded on the eCRF and subject diary.

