### **6.8.10. Dermatologist Global Assessment**

The Dermatologist will assess the local tolerance of the post-procedure skin care regimen in context of the expected effects of the procedure for each subject using the scale below and document the score on the eCRF. To make this assessment, the Dermatologist will draw on the total set of clinical and subject self-assessment data for each subject. The Dermatologist must be unaware of whether a subject was randomized to test product to protect the blind.

Document Name	Protocol 206827 CCI doc		
Type	Version	Document Identifier	Effective Date
elido controlled	4.0; Most-Recent; Effective; CURRENT	090032d580d98eb9	15-Sep-2017 09:27:15
Reason For Issue	Auto Issue		

Rating	Description
0 - Product Regimen was Well Tolerated	No clinically significant worsening of the expected signs/symptoms of the procedure. No new signs/symptoms manifest during product use.
1 - Product Regimen was Not Well Tolerated	Clear, clinically relevant worsening of the severity or frequency of expected signs/symptoms of the procedure and/or any occurrence of new, unexpected signs/symptoms during product use.

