##### **Adverse Event Definition:**

1. An AE is any untoward medical occurrence in a subject or clinical investigation subject, temporally associated with the use of an investigational or washout product, whether or not considered related to the investigational or washout product.
2. NOTE: An AE can therefore be any unfavorable and unintended sign (including an abnormal laboratory finding), symptom, or disease (new or exacerbated) temporally associated with the use of an investigational or washout product.

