#### **9.2.3. Criteria for Evaluation**

The primary evaluation of tolerance will be based on the Dermatologist global assessment. The trial will be considered a success if the majority (i.e. more than 50%) of subjects in the test product group have a favorable Dermatologist global assessment score.

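### The Safety rule in Section 9.2.1 still turns on the assigned group's product, although Section 9.1 records five wrongly treated subjects per group

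*Protocol*

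**What the plan says.** Section 9.2.1 puts all randomised subjects in ITT. For Safety it asks for at least one "application of product in the test phase (i.e. test product for subjects in Group I or sunscreen for subjects in Group II". Sections 3.4 and 5.2 define these as the randomised groups: Group I test product, Group II no treatment.

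Section 9.1, as amended, describes the planned completers as "WITH 40 SUBJECTS PER TREATMENT GROUP WITH 5 SUBJECTS PER GROUP RECEIVING THE INCORRECT TREATMENT DUE TO MIS-ALLOCATION". The Protocol Amendment Page gives the reason for the larger sample as "in response to the first 10 subjects being incorrectly randomised into the study", and lists only the synopsis, Section 3.3 and Section 9.1 as changed.

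Sunscreen is common to both arms. Section 6.4.10 states "All subjects will undergo supervised sunscreen application", and the later visits repeat it. Section 9.2.2 states "No data will be excluded from any analyses". Section 9.3.4 tabulates adverse events by product group without saying whether that means the product assigned or the product received. Section 9.2.3 sets the success rule: "The trial will be considered a success if the majority (i.e. more than 50%) of subjects in the test product group" are rated favourably by the dermatologist.

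**The concern.** A Safety population should contain everyone exposed to study product. The bracket in 9.2.1 gives that result only if each subject used the product of her assigned group. The sponsor knew that ten subjects had not, and changed the sample size for that reason, but left the population rule alone. The rule can therefore misfire on an event that the same document records one section earlier.

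The trial's primary question is local tolerance of the test product. At stake is whether exposed subjects could be left out of the safety tables, and whether reactions on test product could be shown in the no-treatment column.

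**Working it through.** **The plan's own figure.** Section 9.1 claims 80% power for a within-group TEWL change of 1.83 with 40 per group, SD 4.053 and two-sided alpha 0.05. A one-sample t-test on the noncentral t gives 79.5% power, and a detectable change at 80% power of 1.84 (1.795 by the normal approximation). The figure reproduces. The present point is a head count and does not depend on it.

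**Inputs.** From 9.1: 100 randomised, 40 expected completers per group, 5 per group on the incorrect treatment. Assumed: 50 randomised per arm; everyone otherwise starts product; the 5 mis-allocated Group I subjects never applied test product; the 5 mis-allocated Group II subjects did.

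**Safety as written.**
- Group I: 50 − 5 = 45. The five used sunscreen, but the bracket names only test product for Group I.
- Group II: 50, all through sunscreen, including the 5 given test product.
- Total: 45 + 50 = 95 of 100.

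For these five Group II subjects, test product does not count towards entry. Sections 3.4 and 5.2 allow no sunscreen on the day of the peel. So such a subject who applied test product that day and left before the next visit would also fall outside the literal rule.

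**Safety by any product applied, classified by product received.** Test product: 45 + 5 = 50. No test product: 45 + 5 = 50. Total: 100.

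**Adverse events, only if the product groups of 9.3.4 are the randomised groups.** Of 50 test-product users, 5 (10%) are tabulated under no treatment. With an assumed product-reaction rate r, the chance that at least one of the five has a reaction shown there is 1 − (1 − r)^5:

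| Assumed r | Chance |
|---|---|
| 2% | 9.6% |
| 5% | 22.6% |
| 10% | 41.0% |

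**Success rule, only if the test product group of 9.2.3 is the randomised group.** More than 50% of 40 completers means 21 favourable ratings. With k non-users among the 40, the users must supply (21 − k)/(40 − k) if every non-user is favourable, and 21/(40 − k) if none is.
- k = 5, as in 9.1: from 16/35 = 45.7% to 21/35 = 60.0%.
- k = 4, if the five also complete at the planned 80%: from 17/36 = 47.2% to 21/36 = 58.3%.

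The verdict could change only if the favourable rate among users lies within about 4 points below or 10 points above 50%.

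**The case against.** Much of the case on the other side stands.

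- **The opening clause and 9.2.2 point the other way.** Without its bracket, the Safety sentence would admit all ten subjects, and 9.2.2 excludes nothing. That is fair, but the bracket is introduced as a definition. A Safety rule with two tenable readings needs rewording.
- **The exposure is inferred.** The Amendment Page speaks of incorrect randomisation and 9.1 of mis-allocated treatment. Neither says whether the error was corrected during the 14 days. A single later application of test product would bring a Group I subject into Safety even under the literal rule. This stands, and the count of 95 is conditional on it.
- **A reader might infer that the protocol assigns the five Group II users to no treatment throughout.** It does not say so. Section 9.2.1 sets membership, not table columns. Sections 9.2.3, 9.3.2 and 9.3.4 do not distinguish assigned from received product, and a SAP could settle this.
- **A reader might infer that the primary tolerance rate is run on Safety, or concerns test product alone.** Nothing ties that rate to Safety. The favourable rating in 6.8.10 does include "No new signs/symptoms manifest during product use", but it judges the whole post-procedure regimen in both arms. Section 7.1.1 counts events "temporally associated with the use of an investigational or washout product", so events in sunscreen-only subjects are adverse events too.
- **Counting mis-treated subjects in their randomised arm is ordinary ITT practice.** Agreed. Making the rate by product received the headline would change the success criterion after the error was known.
- **Actual exposure can be recovered.** Supervised applications go on the eCRF (6.3.20, 6.4.9) and adverse events are also listed. This limits the harm and makes the correction cheap.

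**Conclusion.** The Safety definition in 9.2.1 was not reconciled with the mis-allocation in 9.1 and, as worded, conflicts with its own opening clause and with 9.2.2. On the assumptions of 50 per arm and no test product ever applied by the mis-allocated Group I subjects, it loses 5 exposed subjects of 100. Display of 10% of test-product users' adverse events under no treatment follows only if product group means randomised group, which the protocol leaves open.

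The documents do not support the stronger conclusion that the success verdict is compromised. The effect on it is small and needs tolerance near 50%. Confidence is moderate, because the exposure history is not stated. The point is minor to should-fix.

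**What to change.** - **Section 9.2.1:** define Safety as all randomised subjects with at least one test-phase application of any study product (test product or sunscreen), whatever the assigned group.
- **Section 9.3.4:** tabulate adverse events by product actually received.
- **Section 9.2.3:** keep the success criterion as planned and state which grouping it uses. Report the tolerance rate by product received as a supplementary analysis only.

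The cost is a few sentences of rewording and one extra table. No new data are needed, since applications are already recorded on the eCRF. The one drawback is two tolerance rates that may differ by a few points. Naming the planned one as decisive in advance deals with that.

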Supervised Test-Product Application 				X	X	X	X	
Supervised Sunscreen Application 				X	X	X	X	
Products and Test Diary Return								X
Discharge from Study								X

 GlaxoSmithKline	Document Name	Protocol 206827 CCI doc		
	Type	Version	Document Identifier	Effective Date
	elido controlled	4.0; Most-Recent; Effective; CURRENT	090032d580d98eb9	15-Sep-2017 09:27:15
	Reason For Issue	Auto Issue		

1. For Visits 3-8, subjects will be instructed to cleanse their face at home using the cleanser provided and must not use any other product on their face, including the test product (Group I only) and sunscreen. Subjects will be instructed to bring the dispensed cleanser, sunscreen and test product (Group I only) with them to all visits. Subjects will be invited to the site in the morning (prior to 9 am) to avoid exposure to strong sunlight.
2. The Investigator or designee will review the diary to monitor and encourage compliance. Additional or missed product applications will be recorded as deviations. The Evaluator must be blind to diary review.
3. Exclusion Criteria 9 will not be included for this assessment. Exclusion criteria 9 is evaluated based on the results from the sensitivity test.
4. To include a review of the inclusion/exclusion criteria specified in Appendix 4. Subjects must be considered compliant with these inclusion/exclusion criteria in order to remain eligible for the study.
5. Peel regimen (70% Glycolic Acid facial peel solution, Bicarbonate Neutralizing Solution and Sunmax Sensitive SPF 50) to be applied to the volar forearm of each subject by a qualified dermatologist.
6. Assessments to be taken 45±15 minutes after completion of the study material sensitivity test.
7. Assessments to be taken 24±4 hours after completion of the study material sensitivity test.
8. Assessments to be taken 7 days after completion of the study material sensitivity test.
9. 70% Glycolic Acid facial peel to be administered by a qualified dermatologist who must be blind to randomization. The Glycolic Acid treatment and neutralizing solution will be sourced commercially by the study site.
10. Assessments to be taken 60±15 minutes after completion of the facial peel procedure.
11. Only subjects randomised to Group I will be dispensed test product. Subjects in Group I and II will be dispensed different test diaries to reflect the difference in treatment allocation. The washout diary will be returned at the same time as test diary dispensing.

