12. Test product application will occur immediately after the post-procedure, pre-treatment (Baseline) assessments are complete and under the supervision of the Investigator or designee to subjects in Group I, only. Subjects in Group II will not apply anything to their face. The Evaluator must be blind to test product application.
13. Measurements to be taken 180±15 minutes, 360±15 minutes, 24±4 hours, 48±4 hours, 72±4 hours, 168±4 hours and 336±4 hours after completion of the facial peel procedure. At Visit 3, there must be at least 30 minutes between test product application (Group I, only) and instrumental measurements.
14. Images to be captured 24±4 hours after completion of the facial peel procedure and at Visit 8 (Day 22).
15. Assessments to be taken 180±15 minutes, 24±4 hours, 48±4 hours, 72±4 hours, 168±4 hours and 336±4 hours after completion of the facial peel procedure.
16. Test product application will be conducted under the supervision of the Investigator or designee to subjects in Group I, only. Subjects in Group II will not apply the test product to their face.
17. Sunscreen application will be conducted under the supervision of the Investigator or designee to all subjects.

Document Name	Protocol 206827 CCI doc	Document Identifier	Effective Date
Type	Version		
eldo controlled	4.0; Most-Recent; Effective; CURRENT	090032d580d98eb9	15-Sep-2017 09:27:15

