Within the washout phase, a study material sensitivity test is included to identify subjects who may be sensitive to the study materials in order to determine whether they are suitable to undergo the facial peel procedure. A qualified dermatologist will dispense a thin layer of the 70% glycolic acid peel solution to cover a demarcated 5 x 5 cm square area on the volar surface of the forearm and, within a period of 30-60 seconds, will neutralize the 70% glycolic acid peel solution with the bicarbonate neutralizing agent and then rinse the skin thoroughly with water and pat dry with a soft towel. Once dry, the dermatologist will apply a thin layer of the Sunmax Sensitive SPF50 Sunscreen to the 5 x 5 cm square area. Dermatologist and subject self-assessments will be used to evaluate local tolerance. If subject data for the study material sensitivity study contains a dermatologist or subject self-assessment score of "Severe" for any attribute, this subject will be deemed to be in violation of exclusion criteria 9 and must be discharged from the study.

Upon completion of the washout phase, subjects considered to be eligible for the test phase will be randomised to two groups (Group I: Test product; Group 2: No-treatment) and a qualified dermatologist with experience administering facial peels will conduct the 70% Glycolic Acid procedure.

Subjects randomised to Group I will be instructed to apply the test product twice-daily (morning and evening) after cleansing, for a total of 14 consecutive days. All subjects will be instructed to continue using the facial cleanser twice-daily during the morning and evening, and to apply the sunscreen in the morning and at lunchtime. A summary of the subject's post-randomization regimen is included below for clarity.

Randomized Group	Morning	Lunchtime*	Evening
Group 1	1. Cleansing 2. Test Product 3. Sunscreen	1. Sunscreen	1. Cleansing 2. Test Product
Group 2	1. Cleansing 2. Sunscreen	1. Sunscreen	1. Cleansing

\*Lunchtime application must be at least 3 hours after previous sunscreen application

Subjects will not apply any sunscreen on the day of the facial peel procedure (Day 8), since they will remain at site until the evening (after 5 pm). On the morning of each visit, prior to arriving at the site, subjects will be instructed to cleanse their face and not to apply any test product or sunscreen until after all measurements and assessments have been completed. Before leaving the site, subjects will undergo

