### **6.3.20. Supervised Test Product Application Post-Procedure**

Subjects randomized to test product (Group I) will be instructed to apply the test product as per the labelled usage instructions immediately after the post-procedure, pre-treatment (baseline) assessments are complete. The Investigator or designee will oversee this initial product application. Group II will not apply any test product. Product application will be recorded on the eCRF and subject diary and must happen at least 30 minutes prior to any further instrumental measurements. The Investigator or designee involved in this step must not be involved in any assessments in order to protect the blind.

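### Section 9.2.1 starts the Safety population about 1 hour after the peel in Group I but about a day after it in Group II, so early leavers may be counted in one arm only

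*Protocol*

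**What the plan says.** Section 9.2.1 of the protocol sets the entry rule: a subject joins the Safety population once she has used the qualifying product in the test phase. That product is the balm in Group I, and the rule names "sunscreen for subjects in Group II". The list is closed, so the cleanser does not qualify anyone.

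The schedule fixes when each qualifying application can first happen.

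- **Baseline on Day 8.** Schedule of Events, footnote 10: "Assessments to be taken 60±15 minutes after completion of the facial peel procedure".
- **Group I.** Footnote 12: "Test product application will occur immediately after the post-procedure, pre-treatment (Baseline) assessments are complete". Section 6.3.20 repeats it: "immediately after the post-procedure, pre-treatment (baseline) assessments are complete".
- **Group II at the same step.** Footnote 12: "Subjects in Group II will not apply anything to their face".
- **Sunscreen on Day 8.** Section 3.4: "Subjects will not apply any sunscreen on the day of the facial peel procedure (Day 8"). Section 5.2 says the same.
- **Later visit mornings.** Section 3.4 tells subjects "not to apply any test product or sunscreen until after all measurements and assessments have been completed". At Visit 4 the supervised sunscreen (Section 6.4.10) is the last of ten steps.

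On the analysis side, Section 9.3.4 plans to tabulate adverse events by product group and to list them, without naming a population. Section 9.2.2 says that no data are excluded from any analysis, and Section 9.2.6 that the available data of dropouts are considered. Section 7.2 collects adverse events in both arms from the sensitivity test at Visit 1 onwards.

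**The concern.** Everyone who undergoes the peel is at risk of an acute reaction to it, whichever arm she is in. A population meant for comparing safety by group should therefore admit both arms at the same moment. Here, a Group I subject is in once she has applied the balm on Day 8, while a control must stay in the study for most of another day.

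The protocol foresees departures in that interval. Section 6.3.14 lets the dermatologist judge a subject unsuitable to continue, and allows discontinuation after reports of discomfort between visits. At Visit 4, adverse events and continued eligibility are reviewed at steps 2 and 3, before the sunscreen at step 10. A control whose reaction is recorded and who is then discharged at step 3 has an adverse event on file but never meets the Safety definition.

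Section 9.2.5 makes reported adverse events part of the tolerance evaluation. If the by-group table rests on this population, entry depends on arm-specific follow-up during the acute period, and the subjects lost would be controls who left early.

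**Working it through.** The protocol gives no figure to reproduce here. The check has two parts: entry times from the visit windows, and an illustration of what the gap could do to a rate.

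**Entry times**

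- Group I: directly after a baseline at 60 ± 15 min, so about 45 to 75 min after the peel.
- Group II: after the Visit 4 assessments at 24 ± 4 h (Sections 6.4.5 to 6.4.8), so no earlier than about 20 to 28 h after the peel.
- Nominal gap: 24 h − 1 h = 23 h.
- Shortest gap: 20 h − 75 min = 20 − 1.25 = 18.75 h.
- Longest gap: 28 h − 45 min = 28 − 0.75 = 27.25 h.

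**Who is treated differently**

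| Subject leaves | Group I | Group II |
|---|---|---|
| before the first balm application (first hour or so) | out | out |
| after that, but before the end of Visit 4 | in | out |
| after the sunscreen at Visit 4 | in, with Day 8 events | in, with Day 8 events |

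Only the middle row is asymmetric.

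**Illustration**

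The protocol plans 100 randomised subjects. Assume 50 per arm and 5 subjects with an adverse event in each arm. Of these 5, assume that k per arm leave in the middle row, that nobody else leaves then, and that the table uses the Safety population. Neither the 5 nor k comes from the documents.

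- Group I rate: 5/50 = 10.0% for every k.
- Group II rate: (5 − k)/(50 − k).

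| k | Group I | Group II | Difference, percentage points |
|---|---|---|---|
| 0 | 10.0% | 5/50 = 10.0% | 0 |
| 1 | 10.0% | 4/49 = 8.2% | 1.8 |
| 3 | 10.0% | 2/47 = 4.3% | 5.7 |

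The true rates are equal in every row. With k = 3, three of the five affected controls (60%) would have to leave before their first sunscreen, and nothing in the protocol points to so high a share. With one common entry event the gap is 0 h and each row returns to 5/50 against 5/50.

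**The case against.** A reader might infer that acute reactions in controls on Day 8 are dropped from the safety results. The documents do not say that. Section 9.3.4 names no population, Sections 9.2.2 and 9.2.6 point towards keeping all data, and the population for each table may properly be set in the statistical analysis plan, which is not at hand. This part stands: the loss is conditional. It does not remove the point, because Section 9.2.1 itself fixes the Safety definition and the adverse event table is its obvious use. The general statements in 9.2.2 and 9.2.6 conflict with the definition and do not repair it.

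The affected group is also narrow. A control who reacts on Day 8, returns and applies sunscreen at Visit 4 is in the population with her Day 8 events. A severe score after the peel is an adverse event but does not by itself require withdrawal; the discharge rule for severe scores concerns the forearm sensitivity test. Subjects also stay on site until 5 PM on Day 8 and are asked back before 9 AM. All of this stands.

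A reader might also take 2 to 6 percentage points as the size of the bias. That range needs an assumed event rate and an assumed share of leavers, and it leaves out zero, which the documents do not rule out.

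Finally, the consequence for conclusions is limited. Success under Section 9.2.3 rests on the global assessment in the test product group alone (more than 50% favourable), and Section 9.3.4 plans no between-arm test of adverse events. The artefact would make the balm look worse, so it cannot produce a falsely favourable claim.

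**Conclusion.** The asymmetry is certain on the protocol's own schedule: entry comes about 23 hours later in Group II than in Group I at nominal times (18.75 to 27.25 hours across the visit windows). Its effect is conditional. It arises only if the adverse event table uses the Safety population and at least one control discontinues between about 1 hour after the peel and the end of Visit 4.

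The protocol gives no count or rate of such departures. The number is probably small and may be zero, and the percentages above show the mechanism and are not an estimate. Any distortion runs against the test product, sits in a descriptive table and does not reach the primary success criterion. It is a drafting defect that is cheap to correct, and Section 9.2.1 needs reconciling with Sections 9.2.2 and 9.2.6 in any case.

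**What to change.** In Section 9.2.1, define the Safety population as all randomised subjects in whom the facial peel was started. In Section 9.3.4, state that the adverse event table uses it.

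State the grouping rule as well. Subjects are grouped by randomised arm, except that the mis-allocated subjects described in Section 9.1 (5 per group) are grouped by the regimen they actually received. A subject who leaves before any post-peel application stays in her randomised arm. Grouping everyone simply by balm or no balm should be avoided: it would move a Group I subject who leaves before her first balm application into the control column, while no control could move the other way for the same reason. That would create a new asymmetry in favour of the product.

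The cost is one or two sentences and no new data. The small downside is that a few Group I subjects never exposed to the balm may be counted in that arm; a footnote to the table can give their number.
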